### Aims & Hypotheses:

**Aim 1:** To determine the impact of increased frequency and intensity of PT services compared to the usual care PT on discharge disposition of patients post-stroke.

**Hypothesis 1:** We hypothesize that patients receiving an increased frequency of PT services will have higher rate of discharging to home/acute rehabilitation center than to a subacute rehabilitation/skilled nursing facility compared to patients in the usual care PT group.

**Aim 2:** To determine the impact of increased frequency and intensity of PT services, as opposed to usual care, on functional mobility.

**Hypothesis 2:** We hypothesize that patients in the treatment physical therapy group will demonstrate higher degree of improvement on the Activity Measure for Post Acute Care (AMPAC) and Postural Assessment Stroke Scale (PASS) from admission to time of discharge from the hospital and at 90-day follow up. We also expect lower overall Modified Rankin Scale (mRS) scores for the increased frequency PT group compared the usual care PT group at three months post stroke.

**Aim 3:** To ensure that high frequency dosage is safe and feasible to implement the proposed PT regimen in the acute inpatient setting.

**Hypothesis 3:** We hypothesize that there will be fewer adverse events experienced by patients in the increased frequency compared to the usual care group.

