#### **4.0 Study Endpoints**

Physical Performance and Functional Measures: PASS scores & AMPAC scores on evaluation, day three, discharge, and 90 day follow up. Discharge disposition recommended vs ultimate discharge disposition, hospital length of stay, and 30-day readmission.

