## **10.0 Study Design:**

This study will be designed as a randomized control trial with a 1:1 randomization. This study will utilize a permuted block design to randomly allocate a participant to a treatment group, while maintaining a balance across treatment groups. All patients will be identified and consented within 24 hours of admission.

The treatment group will receive increased frequency of PT services within the first 3-5 days of admission, followed by daily PT services for the duration of their inpatient stay. As part of the increased intensity of the treatment provided- this group will receive error augmentation training where the treating therapist will induce errors throughout mobility to challenge the patients rather than facilitating error-free movement. The deficits identified on evaluation will be targeted and emphasized throughout all therapy sessions. For patients with hemiparesis, the hemiparetic limb will be resisted during mobility. For patients with balance impairments- balance will be challenged by narrowing the base of support and resisting midline positioning

toward the side of the balance impairment. The treatment as usual group will receive standard care of PT services 3-5 times per week during their hospitalization which focuses on performing bed mobility, transfers and ambulation vs wheelchair mobility as able. Safety will be ensured throughout therapy sessions. Fall risk will be avoided with the use of a gait belt and non-skid socks and cerebral perfusion concerns will be mitigated by checking a resting blood pressure prior to upright mobility. The Postural Assessment Stroke Scale will be obtained as part of the initial PT clinical evaluation, on day three of hospital admission and at 90 day follow up. Follow up will be conducted (at 90 days +/- 15 days) via neurology clinic- either in person, through virtual clinic or, patient will be contacted via password protected Zoom. NIHSS and MRS scores will also be obtained from patient's chart on admission and at 90 day follow up. All of this data will be collected prospectively for both groups for this research study.

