For the primary outcome, PASS, to test the null hypothesis of no difference between the group versus a MCID of 2.7, at 5% significance level, using a repeated measure designs at 4 time points and an autoregressive correlation of .6, and a standard deviation of 720 with more than 80% power. Although there is power to detect a moderately small difference (2.7 as mentioned), the purpose here is also to estimate the difference between the two randomized groups. Based on the past literature, in similar populations the standard deviation of PASS measurements is at the most 7.20 Using this, with a sample of 75 patients in each group, with 95% confidence at the end of the study we can estimate this difference within a margin of error of 2.3.

We are planning to conduct the analysis using intention to treat paradigm. In a preliminary analysis we will compute all summary statistics. Initial plots, such as spaghetti plots, will be used to guide our analyses. A general linear mixed model approach will be used to analyze all the outcomes. This model will account for the correlations between time points using either a compound symmetric or spatial structure for the covariance matrix. Post-hoc analyses using Tukey type adjustments will be performed to obtain least squares estimates of the differences between the two randomized groups. Although the study is powered based on only the primary outcome (PASS), we will apply multiple comparisons adjustments for the rest of the outcomes, using Bonferroni corrections. We will test for the assumptions using diagnostic procedures and take appropriate actions if needed. Also, we will define an outcome to be 'favorable' or 'unfavorable' based on a threshold and apply generalized linear mixed models with logistic link and repeat the analyses. We will attempt to minimize drop- outs but in case of missing data, we will assume Missing at Random or Missing Completely at Random. If necessary we will perform multiple imputations. For all analyses, we will use SAS, (MIXED, GLIMMIX, MI and MIANALYZE).

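### The PASS mixed model names only a compound symmetric or spatial covariance, with no time metric or selection rule, for very unevenly spaced visits; an unstructured covariance is a cheap improvement

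*Combined protocol and SAP*

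**What the plan says.** Section 11.0 (Data Management), which holds the statistical text, calls PASS the primary outcome and models the correlation between time points "using either a compound symmetric or spatial structure for the covariance matrix". It gives no spatial function, no unit of distance and no criterion for choosing. The nearest guidance is that plots will inform the analysis, and this sentence: "We will test for the assumptions using diagnostic procedures and take appropriate actions if needed". The power statement in the same section assumes four time points and "an autoregressive correlation of .6", again without a unit.

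On what is tested, section 11.0 says: "Post-hoc analyses using Tukey type adjustments will be performed to obtain least squares estimates of the differences between the two randomized groups". Hypothesis 2 (section 1.0) instead speaks of improvement on AMPAC and PASS "from admission to time of discharge from the hospital and at 90-day follow up", which is a change from admission.

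The schedule is given in two ways. Section 4.0 lists "PASS scores & AMPAC scores on evaluation, day three, discharge, and 90 day follow up", which is four visits. Section 10.0 has PASS at the initial evaluation, "on day three of hospital admission and at 90 day follow up", which is three, and its data-collection list also omits discharge. The follow-up window is 15 days either side of day 90.

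**The concern.** Two or three of the visits fall within one hospital stay and the last is about three months later. Compound symmetry gives every pair of visits the same correlation. A spatial structure in days makes correlation decay with elapsed time, so day 90 becomes almost independent of the inpatient visits. A spatial structure by visit order treats the long gap as one step. These are three different models, and an analyst could choose any of them and still comply with the plan.

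With complete data and group-by-visit means the estimates are the same under all three, but the standard errors are not. At stake is whether a nominal 5% PASS test really runs at 5%. The answer depends on the unstated metric and on a contrast that section 11.0 does not name.

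**Working it through.** **Inputs from the documents.** 75 per arm, 5% level, difference 2.7, four time points and autoregressive 0.6 (section 11.0); SD 7 (section 6.0; the SD printed in section 11.0 is read as the same 7 with a reference number run into it, and 7.2 is used as a check).

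**Assumptions.** Two-sided test, equal SD at every visit, complete data, model-based standard errors, evaluation on day 0 or 1, discharge on day 4, 6 or 9. Except in step 6, the true correlation is 0.6 per visit step.

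**1. The plan's power.** The entries of the four-visit correlation matrix sum to 4 + 2(3×0.6 + 2×0.36 + 0.216) = 4 + 2×2.736 = 9.472. The SD of the visit average is 7√(9.472/16) = 5.39 and its SE is 5.39√(2/75) = 0.880. Power is Φ(2.7/0.880 − 1.96) = 86.6% (84.7% at SD 7.2). A single visit gives 65.6%. The stated 80% or more therefore fits a visit-averaged difference.

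**2. Compound symmetry.** The fitted common correlation is the mean of the true ones: 2.736/6 = 0.456 for four visits, (0.6 + 0.6 + 0.36)/3 = 0.52 for three. The actual level is 2[1 − Φ(1.96 × model SE/true SE)].
- Change to 90 days, four visits: √((1 − 0.456)/(1 − 0.216)) = 0.833, level 10.3%.
- Change to 90 days, three visits: √(0.48/0.64) = 0.866, level 9.0%.
- Change to discharge, four visits: √(0.544/0.64) = 0.922, level 7.1%.
- Visit-averaged difference: 4 + 12×0.456 = 9.472, the same as the truth, so 5%. The 90-day difference uses only the variance at that visit, so also 5%.

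**3. Spatial in days, no subject effect.** Day-90 correlations are close to zero; the inpatient ones are taken as correctly fitted.
- Change to 90 days: √(1/0.784) = 1.13, level 2.7%; three visits √(1/0.64) = 1.25, level 1.4%.
- Visit-averaged: √((4 + 2×1.56)/9.472) = 0.867, level 8.9%; three visits √((3 + 2×0.6)/(3 + 2×1.56)) = 0.828, level 10.4%.

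**4. Spatial in days plus a random intercept.** Fitted by likelihood to the same true matrix over the assumed days, this gives about 5% for the visit-averaged difference and 7.7 to 8.9% for the change to 90 days.

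**5. Simulation.** 40,000 trials, REML refitted in each, t on 148 degrees of freedom, no multiplicity adjustment:

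| Structure fitted | 90-day difference | Visit-averaged | Change to 90 days |
|---|---|---|---|
| Compound symmetry | 4.7–4.9% | 4.9–5.1% | about 10% (4 visits), 9% (3 visits) |
| Spatial, visit order | 4.7–5.0% | 4.7–5.0% | 4.7–5.0% |
| Spatial, days, no subject effect | 4.6–4.8% | 8.8–10.4% | 1.4–2.6% |
| Unstructured | 4.8–5.1% | 4.8–5.1% | 4.8–5.1% |

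Suppose the structure is chosen by REML likelihood. Against spatial by visit order, compound symmetry wins in under 0.1% (four visits) or 1.0% (three) of trials, and the change test is then 4.8 to 5.0%. Against spatial in days without a subject effect it wins in 72 to 97% or 99.9%, and the change test is 8.2 to 9.8% or 8.7%.

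**6. The other reading: 0.6 per day.** Spatial in days is then correct, and day 90 is uncorrelated with the rest. Under compound symmetry, visits on days 1, 3, 4 and 90 have mean correlation (0.6² + 0.6³ + 0.6)/6 = 0.196; √(1 − 0.196) = 0.897, level 7.9%. Visits on days 0, 3, 9 and 90 have mean (0.6³ + 0.6⁹ + 0.6⁶)/6 = 0.045; √(1 − 0.045) = 0.977, level about 5.5%.

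**7. Cost and power.** If compound symmetry at 0.6 were true, power for the change is 74.7% on 148 degrees of freedom (unstructured) against 75.0% on 444 (compound symmetry). For the change to 90 days under autoregressive 0.6 by visit order, the SD is 7√(2×0.784) = 8.77, the SE is 8.77√(2/75) = 1.43, and power is Φ(2.7/1.43 − 1.96) = 47%.

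**The case against.** The strongest reply is that section 11.0 describes differences between the randomised groups, and for those compound symmetry is harmless. This stands. A reader might infer that compound symmetry doubles the error rate of the primary PASS analysis as written. The documents do not support that: the inflation belongs to the change from admission, which comes from Hypothesis 2 and is not written in section 11.0 as the PASS test.

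Second, the result needs the planning correlation to run by visit order, and section 11.0 does not say so. This also stands. Under that reading spatial by visit order is correct and a routine fit comparison finds it. Read per day, the inflation is smaller.

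Third, a mixed model may carry a subject effect. With a random intercept, the days structure no longer distorts the visit-averaged test, and the change test turns from conservative to liberal. So it would be too strong to say that any spatial structure in days fails for the visit-averaged difference.

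Fourth, the sentence on diagnostics leaves room for another structure. True, but it states no criterion and no alternative, so it is not a selection rule.

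The multiplicity adjustments do not bear on this. With two groups, Tukey's critical value equals that of the t test (1.976 on 148 degrees of freedom). Section 11.0 applies Bonferroni only to outcomes other than PASS.

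**Conclusion.** The point holds as a worthwhile, low-cost improvement and not as a fatal flaw. The plan names two structures, with no time metric and no rule, for visits where the metric matters greatly. Under autoregressive 0.6 by visit order, complete data and 75 per arm, compliant choices put the admission-to-90-day change test anywhere from about 1.4% to about 10%, and the visit-averaged test at about 5% or at 9 to 10%. The unstructured covariance stayed at 4.8 to 5.1% throughout.

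The arithmetic is firm; how far it applies depends on that reading of the planning assumption and on which contrast is tested. Discharge day and evaluation day are assumptions. The simulations used 148 degrees of freedom and not Kenward-Roger. With incomplete data, which the withdrawals in section 12.0 make likely, the covariance would affect the estimates as well as the standard errors.

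A reader might also infer that naming the Hypothesis 2 contrast is equally cheap. It is not: the stated power fits a visit average (about 86% at SD 7), and the simple change to 90 days has about 47%.

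**What to change.** In section 11.0, replace the two-structure wording with an unstructured covariance over the scheduled PASS visits, visit as a categorical factor, and Kenward-Roger degrees of freedom. State one fallback for non-convergence, for example AR(1) by visit order with robust standard errors. If the two structures are kept instead, state the time metric and the information criterion for choosing.

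The cost is one or two sentences and TYPE=UN in the SAS MIXED procedure already named. There are 10 covariance parameters for four visits or 6 for three, against 2 for either named structure in its simplest form, with 150 patients. The power loss in the check above is under half a point, and the risk of non-convergence is small.

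Two related matters are separate from this cheap change:
- Name the PASS contrast and time point. If it is the change in Hypothesis 2, restate the power for that contrast.
- Reconcile the four-visit schedule (sections 4.0 and 11.0) with the three-visit schedule (section 10.0). This fixes the dimension of the matrix and settles whether a change to discharge can be estimated.

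### Holm's procedure would be a cheap improvement on the valid Bonferroni correction for the secondary outcomes, with a gain for Aim 1 between nil and about 11 points on assumed inputs

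*Combined protocol and SAP*

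**What the plan says.** The statistical text stands in section 11.0 (Data Management). PASS is named as primary and tested "at 5% significance level", "with more than 80% power", for a difference of 2.7 points. The same section says that the study is powered on PASS alone. For everything else, "we will apply multiple comparisons adjustments for the rest of the outcomes, using Bonferroni corrections".

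The members of that group have to be pieced together:

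- Aim 1 in section 1.0 concerns the effect "on discharge disposition of patients post-stroke".
- Hypothesis 2 adds AMPAC and mRS.
- Hypothesis 3 adds a comparison of adverse events.
- Section 4.0 adds "hospital length of stay, and 30-day readmission", and lists AMPAC at evaluation, day three, discharge and 90 days.

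Section 11.0 also plans to cut outcomes into favorable and unfavorable and repeat the analyses. It does not give the number of tests in the family, the family-wise level, whether time points count separately, or whether the repeats count. No event rate, effect size or power is given for disposition or any other secondary outcome.

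**The concern.** Read naturally, the plan divides the error rate by the number of secondary tests and holds each test to that one threshold. Holm's procedure starts at the same threshold but relaxes it after each rejection, with the same guarantee on family-wise error. Where several outcomes respond together, as Hypotheses 1 and 2 expect, Bonferroni can miss effects that Holm would declare. Aim 1 is exposed to this because disposition sits in the secondary family although it is the first-listed aim.

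A related practical point is that both methods need a known number of tests. With the family unlisted, the divisor could be settled after results are seen.

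**Working it through.** **1. The plan's own figures.** The plan has none for the secondary family. Those for PASS reproduce and are untouched by this point. Section 6.0 prints the standard deviation as 7 with a superscript 20, and section 11.0 prints it as 7.20, so both readings are used.

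- Margin of error with 75 per group: 1.96 × 7.2 × √(2/75) = 2.30. With SD 7.0 it is 2.24, or 2.26 using t. The plan states 2.3.
- Power for 2.7 points, "using a repeated measure designs at 4 time points and an autoregressive correlation of .6": the variance factor for the mean of four measures is [4 + 2(3×0.6 + 2×0.36 + 0.216)]/16 = 0.592. The standard error is 7.2 × √0.592 × √(2/75) = 0.905, and power is Φ(2.7/0.905 − 1.96) = 84.7%. With SD 7.0 it is 86.6%. The plan states more than 80%.

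**2. Why Holm never rejects less.** Order the p-values from smallest to largest. Holm compares them in turn with 0.05/m, 0.05/(m−1), and so on up to 0.05, and stops at the first failure. With m = 5 the thresholds are 0.010, 0.0125, 0.0167, 0.025 and 0.05. Bonferroni uses 0.010 throughout. Any p-value at or below 0.05/m, and every smaller one, passes its Holm threshold, so Holm rejects all that Bonferroni rejects. The first step is the same, so the chance of at least one rejection is identical.

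**3. Bonferroni power for one outcome.** Assume 80% power when tested alone at two-sided 0.05. The test statistic then has mean 1.960 + 0.842 = 2.802. At m = 5 the critical value is 2.576, and power is Φ(2.802 − 2.576) = Φ(0.226) = 59%. The divisor matters: the same test has about 62% at m = 4, 57% at m = 6 and 54% at m = 7.

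**4. Holm against Bonferroni for Aim 1.** Simulation of 200,000 trials per scenario. Assumed: m = 5, 80% single-test power for each affected outcome, family-wise level 0.05, correlation between test statistics 0, 0.3 and 0.5.

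| Outcomes truly affected | Bonferroni | Holm |
|---|---|---|
| Disposition only | 59% | 59% |
| Three of five | 59% | 63% |
| All five | 59% | 69% to 71% |

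At correlation 0.3 the pairs are 59.0% and 59.1%, 58.9% and 62.8%, and 59.0% and 69.5%. Family-wise error stayed below 0.05 for both methods.

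**5. Range.** Over m = 4 to 7 and correlation 0 to 0.5, at 80% single-test power, Holm's gain for Aim 1 was 0 to 0.2 points if only disposition is affected and about 2 to 4 points if about half the outcomes are. If all are affected, it was about 5 to 13 points as single-test power ran from 60% to 90%.

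**6. How much of the loss Holm can recover.** The disposition rates here are assumed, with 75 per arm. For 60% against 80%, power is 76.7% at 0.05 and 53.9% at 0.01. For 60% against 75%, it is 50.0% and 26.7%. Holm wins back part of that drop only when other members of the family are rejected first.

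**The case against.** The strongest reply is that Bonferroni is valid, stated in advance and simple, and that secondary outcomes were never promised any power. That stands. A reader might infer that the plan contains a statistical error; it does not, and no stated figure changes.

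A reader might also infer that Bonferroni wastes power on Aim 1 whatever the results, or that Aim 1 is shown to be underpowered. The documents support neither. If only disposition responds, the gain is about a tenth of a point. With no rates for disposition in the plan, its power is unknown. Most of any loss comes from putting an outcome without its own sample-size basis into a shared family, which Holm does not cure. On the other side, Hypotheses 1 and 2 expect benefit on disposition, AMPAC and mRS, and section 14.0 mentions a possibly shorter stay. The case of three or more affected outcomes is therefore the one that the sponsor itself expects.

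Bonferroni also gives simple simultaneous intervals that agree with its tests, and Holm does not. This stands as a small cost. The sentence in section 11.0 about estimating the group difference concerns PASS, which lies outside the family, and no simultaneous intervals are planned for the secondary outcomes.

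Finally, it is a conjecture that the favorable/unfavorable repeats would enlarge the family. The plan does not say whether they count.

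**Conclusion.** This is a minor point of efficiency. Holm gives the same family-wise protection as Bonferroni under any dependence and never rejects fewer hypotheses, so it is the better default for testing the secondary outcomes. On five assumed outcomes with 80% power each, Aim 1 power moves from 59% to between 59% and about 71%, depending on how many of the other outcomes are truly affected. About 63% goes with three of five. The family size, single-test power and correlations are all assumptions, so these figures show the pattern and do not measure this trial's loss. The comparison of the two methods does not depend on them. Listing the family is needed whichever method is kept.

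**What to change.** In section 11.0, name Holm's step-down procedure at a family-wise two-sided 5% in place of Bonferroni corrections. Before any unblinded analysis, the sponsor should add:

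- a list of the family members, with one test and one time point per outcome, chosen with reference to Hypotheses 1 to 3. This includes which AMPAC assessment is used and whether the adverse-event comparison belongs; both choices are the sponsor's.
- a statement whether the favorable/unfavorable repeats are supportive and outside the family.
- the intervals to be reported: 95% intervals labelled as unadjusted, or Bonferroni intervals labelled as conservative (at m = 5, each at 1 − 0.05/5 = 99%).

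The cost is a few sentences, with no change to sample size, data collection or the PASS analysis. The one loss is the exact match between simple simultaneous intervals and the tests.

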## **12.0 Withdrawal of Subjects:**

Subjects will be withdrawn from the research without their consent with the occurrence of worsening medical status, medical instability that limits ability to progress mobility or transfer to the ICU. For subjects who request to withdraw from the research trial, investigators may retain and analyze already collected data relating to that subject.

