Precaution will be taken to lessen the probability of risks; despite increased frequency of treatments, duration of upright will still be approached cautiously within the first 24 hours s/p stroke for cerebral perfusion. ALL stroke patients will be returned to supine within 24 hours post stroke and maintain head of bed <30 degrees except for medication, meals, and therapy. Therapy will be stopped if patient deemed medically unstable for increased frequency of treatments by the Stroke NP, Attendings, Fellow, or PI; this decision will be documented via "bed rest" orders in the patient's electronic medical chart, so that the study team is aware to avoid progressive frequent upright mobilization.

**Data collection:** Patient data will be collected from their medical record. Data collected from EPIC/patient's MUSC EMR will be coded in the research database. Data collected include:

- 1) Demographics: sex, age, race
- 2) Stroke risk factors: history of HTN, HLD, A-fib, or DM
- 3) Stroke specifics: type of stroke (hemorrhagic vs ischemic), location of stroke, stroke severity (measured by NIHSS & MRS), time of symptoms to presentation, intervention (tPA or thrombectomy) and complications
- 3) Physical Performance and Functional Measures: Postural assessment stroke scale scores on evaluation, day three and 90 day follow up. Discharge disposition recommended vs ultimate discharge disposition, hospital length of stay.

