## **13.0 Risks to Subjects:**

Early mobilization in the acute stroke population may pose risks including but not limited to falls, decreased cerebral perfusion, worsening weakness and/or worsening stroke. The research team will monitor blood pressures before each PT session to make sure it is safe for the individual to participate. A confidentiality breach is also a risk associated with this research. However, no paper records will be stored or reviewed other than consent forms and only coded data will be used for the analysis. Identifying information will be removed from the primary database. Identifying information will be stored in a separate file with a unique identifier assigned to the patient to link the two datasets.

The treatment you receive may prove to be less effective or to have more side effects than the other study treatment(s) or other available treatments. The experimental treatments may have unknown side effects. The researchers will let you know if they learn anything during the course of the study that might make you change your mind about participating in the study.

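### Followed as written, Section 12.0 ends research participation when a patient deteriorates, so later PASS and AMPAC go missing for a prognostic reason that the planned MAR/MCAR analysis cannot absorb

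*Combined protocol and SAP*

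**What the plan says.** Section 12.0 is worded as a rule: "Subjects will be withdrawn from the research without their consent with the occurrence of worsening medical status". It also names instability that limits progress with mobility, and ICU transfer. Its only sentence on data covers a different group, those who ask to leave: "For subjects who request to withdraw from the research trial, investigators may retain and analyze already collected data relating to that subject".

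Section 10.0 has a separate rule for an overlapping event, and that rule ends treatment only: "Therapy will be stopped if patient deemed medically unstable for increased frequency of treatments". It is recorded through bed-rest orders and is silent on later assessments.

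Section 4.0 schedules PASS together with "AMPAC scores on evaluation, day three, discharge, and 90 day follow up". Sections 7.0 and 10.0 describe the 90-day contact in clinic or by Zoom without mentioning withdrawn patients. On sources, Section 10.0 says "Patient data will be collected from their medical record".

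The analysis text in Section 11.0 says "We are planning to conduct the analysis using intention to treat paradigm" and "in case of missing data, we will assume Missing at Random or Missing Completely at Random". It plans a mixed model, with multiple imputation if necessary. It names no imputation variables and no sensitivity analysis for informative missingness.

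Section 13.0 lists as risks of early mobilisation "falls, decreased cerebral perfusion, worsening weakness and/or worsening stroke".

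**The concern.** The withdrawal trigger occurs after randomisation, predicts a poor outcome and overlaps the risks that the protocol attributes to mobilisation. Hypothesis 3 itself expects adverse events to differ between arms. If such patients leave the research, their later PASS and AMPAC are missing because they deteriorated, and the 90-day contact and later adverse events (Aim 3) may be lost too.

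MCAR cannot hold when worsening causes the missingness. MAR would require that, given the observed data, withdrawn patients resemble those who stayed. That is implausible for a model with no deterioration variable. A deterioration flag alone would not repair this: if every deteriorated patient is withdrawn, none has a later PASS from which the model could learn.

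The later PASS comparison is biased whenever the share withdrawn times the PASS deficit differs between arms. More deterioration in the intervention arm would flatter it; less would work against it. A score that was never assessed cannot be recovered at analysis.

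**Working it through.** **The plan's own figure.** Section 11.0 gives a 95% margin of error of 2.3 with 75 per arm. With SD 7.2: 1.96 × 7.2 × √(2/75) = 2.30, which reproduces it. (SD 7 gives 2.24; the power sentence prints 720, which would give 230.) The figure assumes that all 75 per arm are analysed.

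**Inputs from the documents.** Four PASS visits (Sections 4.0 and 11.0), autoregressive correlation 0.6, SD 7.2, 75 per arm, MCID 2.7.

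**Assumptions.** The withdrawn shares pT (intervention) and pC (control) and the deficit D in PASS points are not in the documents. D = 7.2 is 1 SD. Half of withdrawals are taken to occur before day 3 and half between day 3 and discharge, with nothing observed afterwards.

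**Formula.** Deterioration lowers the true arm mean by p × D. A MAR analysis predicts the missing scores from patients who stayed, so it leaves that drop out. Positive bias favours the intervention:

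- Drop never observed: bias at day 90 = pT·DT − pC·DC.
- Drop already visible at day 3 in the later half: the model carries 0.6² = 0.36 of it two visits forward, so the bias is multiplied by 1 − 0.5 × 0.36 = 0.82.

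| Withdrawn, intervention vs control | D | Never observed | Partly visible | Share of 2.7 |
|---|---|---|---|---|
| 20% vs 10% | 7.2 | 0.72 | 0.59 | 22-27% |
| 15% vs 10%, or 10% vs 5% | 7.2 | 0.36 | 0.30 | 11-13% |
| 5% vs 2.5% | 7.2 | 0.18 | 0.15 | 5-7% |
| 10% vs 20% | 7.2 | −0.72 | −0.59 | sign reversed |
| 15% vs 15% | 7.2 vs 3.6 | 0.54 | 0.44 | 16-20% |
| 20% vs 10% | 3.6 vs 7.2 | 0 | 0 | offsetting |
| Equal rates, equal D | any | 0 | 0 | none |

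D = 3.6 in both arms halves the first four rows.

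**Simulation check.** 6,000 trials of 75 per arm, analysed with a likelihood-based mixed model with known covariance and compared with full follow-up, gave 0.73 and 0.59 for 20% vs 10%, 0.36 and 0.29 for 10% vs 5%, and −0.72 and −0.57 for 10% vs 20%. A separate simulation in which withdrawn patients contribute only the evaluation score shows the mechanism: with 15% vs 5% withdrawn and D = 7.2, the true difference was −0.75 and the MAR estimate −0.02.

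**Other readings of the schedule, 20% vs 10%, D = 7.2.** Section 10.0 lists three PASS visits, without discharge. Day 3 is then one visit before day 90, and the lower end becomes 0.72 × (1 − 0.5 × 0.6) = 0.50. If the four-visit average is the target, the simulated bias is 0.45 (never observed) or 0.35 (partly visible), 13-17% of 2.7.

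**Can chart data rescue it?** Suppose the 90-day mRS is kept for withdrawn patients and used in imputation, with correlation r to 90-day PASS. Treat it as PASS plus noise of relative variance v = 1/r² − 1. Its regression weight is b = (1 − ρ²)/(1 − ρ² + v), where ρ is the correlation of 90-day PASS with the last observed PASS: 0.6³ = 0.216 for early and 0.36 for later withdrawals.

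- r = 0.5: v = 3 and b = 0.241 and 0.225. Never observed: 0.72 × (0.759 + 0.775)/2 = 0.55. Partly visible: 0.72 × (0.759 + 0.775 × 0.64)/2 = 0.45.
- r = 0.8: v = 0.5625 and b = 0.629 and 0.607. Never observed: 0.27. Partly visible: 0.22.

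The bias shrinks to 0.22-0.55 but does not vanish.

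**The case against.** The strongest objection is that leaving the research could mean only leaving the study regimen. Section 10.0 stops therapy for a similar event, and Section 11.0 plans intention to treat and promises to limit drop-out. That makes the intent unclear, but it does not supply an assessment schedule. If staff would follow these patients anyway, the amendment merely records practice.

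Several narrower points stand. Section 12.0 removes nobody from the analysis set, and earlier visits can stay in the mixed model, so intention to treat is weakened rather than contradicted. MAR is untestable and not logically excluded. Disposition, length of stay, mRS, NIHSS and recorded adverse events are less exposed because they come from the chart, although the plan does not say they will be used for withdrawn patients. Section 10.0 lists PASS among the record data too, but the chart can hold only scores that someone assessed. Consent pages were not in the text reviewed and might address data use after withdrawal; the missing assessment schedule would remain.

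On size, no passage makes day 90 the primary time point, and the medical-stability criterion should lower the withdrawal rate. The standard error behind the 2.3 margin is 2.30/1.96, about 1.18, so even 0.72 is about 0.6 standard errors. This limits how large a problem can be claimed, not whether there is one.

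**Conclusion.** The concern holds, with high confidence in the textual gap. Sections 10.0 and 12.0 treat overlapping events differently, and under Section 12.0 as written the primary outcome is lost because of deterioration. MCAR is ruled out, and MAR is implausible for the analysis described.

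The amount and sign of bias cannot be derived from the documents. Under the assumed range of 5% vs 2.5% to 20% vs 10% withdrawn with a 1-SD deficit, the day-90 bias is about 0.15 to 0.72 PASS points, and it is zero if rates and deficits match. It is a modest, avoidable bias that multiple imputation under MAR would remove only in part. This is a cheap improvement, best made before more patients are withdrawn.

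**What to change.** Reconcile Sections 10.0 and 12.0 so that stopping study therapy is separate from leaving data collection. The clinical criteria for stopping stay with the investigators. Suggested wording:

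> Stopping study therapy does not end data collection. All randomised participants are followed to 90 days by chart review and the planned clinic or Zoom contact unless they withdraw consent to data collection, and are analysed as randomised.

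Count adverse events to 90 days whatever the therapy status, and report withdrawals by arm, timing and reason.

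Useful but secondary:

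- Name chart NIHSS, mRS and complications as imputation variables for PASS that is still missing.
- Add a delta-adjusted sensitivity analysis for data missing not at random, with deaths handled separately.
- Clarify how the ICU as a study setting (Section 7.0) fits with ICU transfer as a withdrawal trigger (Section 12.0); the two can be compatible.

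The cost is an amendment, consent wording on continued data collection, and modest follow-up. At an assumed 5-20% withdrawal this is 0.05 × 150 = 7.5 to 0.20 × 150 = 30 patients, about 8 to 30, through contacts already planned.
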